Control Arm: Infant will receive pressure regulated breaths, 40-60 breaths/min, PiP of 20-24cm of H₂O as recommended by 2017 Neonatal Resuscitation Program (NRP) guidelines. Reading of the TV will be blinded from the providers as in routine clinical situations

Intervention Arm: Infants in the intervention arm will receive VTV following intubation. Peak inspiratory pressure (PiP) provided via T-piece resuscitator will be visible to the providers, and the provider can regulate the PiP to achieve the desired TV goal (4-6 ml/kg), at a rate of 40-60 breaths/min according to a predefined protocol

The infants will continue to receive respiratory support as assigned by the study arm for the first 48 hours of life, following which they will receive routine VTV and weaning as per standard of care NICU practice.

BLINDING

Phase I: Providers will be blinded from the measured TV during the resuscitation.

Phase II: Due to the providers being aware of ventilation process and the need for change in ventilator settings based on the infant's TV, blood gas, blinding the providers will not be possible. Acknowledging this, we will be blinding the outcome assessment. The individual collecting the data for the two groups and performing the physiologic BPD testing will be blinded on the infant's randomization status. Need for discharge home on oxygen will be assessed by a physician not associated with the study and strict guidelines will be followed for discharge home on oxygen. Provider performing long term outcome assessment will also be blinded from the infant randomization status during the study.

PRIMARY OUTCOME VARIABLE

Phase I: Successful measurement of tidal volume in within 60 seconds of intubation and initiation of PPV.

Phase II: Timing of initiation of VTV will be similar to PLV.

STUDY ENDPOINTS

The study patient will continue in the randomized arm for the first 48 hours of life with ongoing data collection for the first 48 hours after initial neonatal resuscitation. After the first 48 hours, infant will continue standard of care per the NICU providers, with continued data collection for longer term outcomes.

SAMPLE SIZE

Phase I: We will select a convenience sample of 10 successive patients for the initial phase of the study.

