Phase II: We will enroll a total of 30 patients (15 per study group). The sample size was selected to insure sufficient number of patients to estimate variability and effect sizes^{xxi} and to estimate recruitment rates. For example, with 30 patients, the width of the 95% confidence will be about 55% as wide as the standard deviation. This estimate will help develop sample size estimates for future studies.

DATA COLLECTION AND STORAGE

Study data will be collected and managed using a secure, web-based, password protected RedCap (Research Electronic Data Capture) data base^{xxii}. Baseline demographic maternal and infant characteristics, TV, PiP, mean airway pressure, PEEP, FiO₂, resuscitation details, duration of invasive mechanical ventilation, duration of non-invasive respiratory support (non-invasive mechanical ventilation, continuous positive airway pressure), duration of oxygen treatment, home O₂ requirement, BPD incidence and severity along with pulmonary complications will be collected. Standard BPD definition of mild (oxygen use for 28 days), moderate (oxygen need at 36 weeks), or severe (ventilatory support at 36 weeks), along with physiologic BPD testing at 36 weeks will be used to define BPD. This data will also be used prospectively in a future randomized control trial if feasibility study is successful. The research team members and DSMB will have access to the full data set.

DATA ANALYSIS

As the study is designed as a pilot, no formal tests of hypotheses will be conducted^{xxiii}. In Phase I, our goal is to attain skill and competency with using the device, as well as to establish that our measures are reliable and valid. Descriptive statistics will be use to assess the feasibility of measuring TV in the DR. Feasible will be defined as being able to successfully measure the TV in 80% of the infants within 60 seconds of starting PPV via the endotracheal tube.

For Phase II of the pilot project, data analysis will be limited to point estimates (e.g., means and proportions). We will describe the feasibility of using VTV in the DR, and data analysis will be limited to estimating the point estimates (e.g., means and proportions) and variability of ventilatory measures in each group and overall. We will also estimate recruitment and attrition rates, as well as the duration of the consenting process.

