We will use the pilot phase to begin identifying and assessing the frequency of adverse events for developing safety measures. Additionally, the pilot data will be used to estimate effect sizes and variability so that sample size and statistical power may be computed for a later randomized control trial.

Although this study will not be powered to evaluate differences in longer term pulmonary outcomes like BPD, we will still assess for possible trends in difference of BPD and other pulmonary outcomes between the two groups. Being a feasibility study, this study will not be powered to evaluate the safety and other long term outcomes between the two arms, but we will collect and analyze the safety data especially since we will be using the enrolled patient data for the future randomized control trial.

VULNERABLE POPULATION

This study involves studying newborn infants, who are considered vulnerable population. In phase I, the subjects involved in the study will have minimal risks as they will receive standard of care practices and we will only assess our ability to measure the TV in this population. In Phase II, the control arm has minimal risk as they will receive standard of care practices. The intervention arm may potentially have direct benefit as with the information about TV during resuscitation, we can target our PiP for goal TV, thereby minimizing volutrauma and/or atelectotrauma. Thus, overall this study poses none to minimal risk for the study subjects and may potentially benefit the infants in the intervention arm.

For the Phase II the study related interventions will be done only after a written informed parental consent has been obtained.

DATA AND SAFETY MONITORING

Safety data will be monitored closely for all enrolled subjects with special focus on infants randomized to the intervention arm in Phase II. Subjects in the intervention arm, based on the tidal volume generated, the maximum PiP will be limited at 30cm of H₂O, as it would be considered unconventional to require more PiP than 30cm of water in the immediate neonatal phase for longer than 60 seconds duration. If the tidal volume cannot be measure within 60 second, the patients will continue to receive conventional PLV during the time eliminating any potential harm to the patient. We will monitor for development of any pulmonary complication in the enrolled subjects including but not limited to pneumothorax, pneumo-mediastinum, and pulmonary interstitial emphysema.

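### Blinding of the 36-week BPD test is stated but not secured: one individual is given both the test and data collection, and the trial's data can reveal the arm

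*Combined protocol and SAP*

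**What the plan says.** The BLINDING section of the combined protocol and SAP concedes that Phase II providers cannot be blinded and answers this by blinding the assessment of outcomes. It sets out three provisions:

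- For data collection and the BPD test: "The individual collecting the data for the two groups and performing the physiologic BPD testing will be blinded" to the infant's allocation.
- Discharge on home oxygen is decided by a physician from outside the study, under strict guidelines.
- The provider doing the long-term assessment is also said to be blinded.

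DATA COLLECTION AND STORAGE lists what is recorded, beginning with "Baseline demographic maternal and infant characteristics, TV, PiP, mean airway pressure, PEEP, FiO₂, resuscitation details, duration of invasive mechanical ventilation" and running on to BPD incidence and severity. It places the physiologic BPD test at 36 weeks. It also states that research team members and the DSMB may see the full data set.

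INTERVENTION separates the arms for two days: "The infants will continue to receive respiratory support as assigned by the study arm for the first 48 hours of life". After that all infants receive routine VTV. STUDY ENDPOINTS keeps data collection running through the same 48 hours.

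**The concern.** In a trial with unblinded providers, masking the person who performs the BPD test is the stated protection for that outcome. Here the masked person is also given the task of collecting data for both groups, and no provision keeps arm-revealing records away from that person.

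If the tester knows or can work out the arm, that knowledge could affect how and when the test is done and how severity is coded. The plan does not describe the test procedure, so the room for judgement cannot be assessed from the documents.

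The stake in this pilot is modest, but the data have a later use. DATA COLLECTION AND STORAGE and DATA ANALYSIS both say they will be used in a future randomized trial, and effect sizes from the pilot are to feed that trial's sample size. A BPD classification made without effective masking cannot be repaired afterwards.

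**Working it through.** No sample size, power or alpha figure in the plan depends on this point, so the check is a comparison of sections.

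**Step 1: who collects and who tests.** The BLINDING sentence uses the singular for one person with both tasks. No other section divides them.

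**Step 2: what the data tell the collector.**

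| Item to be collected | Where | What it reveals |
|---|---|---|
| Timing of starting VTV relative to PLV | PRIMARY OUTCOME VARIABLE, Phase II | Recording it means recording which mode was started |
| PiP successfully adjusted to goal tidal volume (TV) | SPECIFIC AIMS, Phase II, Aim 1 | Applies to the intervention arm; control providers do not see TV |
| VTV failure and switch to PLV | SPECIFIC AIMS, Phase II, Aim 1; Withdrawal/Termination Criteria | Intervention arm only |
| PiP, mean airway pressure, PEEP and oxygen over 48 hours | SPECIFIC AIMS, Phase II, Aim 2 | Suggests the arm |
| TV values | RANDOMIZATION | Suggests the arm; TV is measured in both arms |

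The first three rows label an arm or exist for only one arm. The last two are weaker cues. The control instruction is "Control Arm: Infant will receive pressure regulated breaths, 40-60 breaths/min, PiP of 20-24cm of H₂O", while in the intervention arm PiP is varied to reach 4-6 ml/kg and "the maximum PiP will be limited at 30cm of H₂O". The two PiP patterns can overlap at 20-24, and a control infant's TV can fall within 4-6 ml/kg. These values therefore allow a guess but not a certain identification.

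**Step 3: is there a barrier?** The plan describes no role split, masked abstraction, automatic transfer of monitor data or restricted REDCap form. The only statement on access is that the research team has the full data set. Whether the BPD tester counts as a team member is not stated, and nothing excludes that person.

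**Step 4: which outcomes are exposed.** Discharge oxygen and long-term assessment are assigned to other people under separate provisions. The physiologic BPD test is the one assessment tied to the combined role.

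**Step 5: scale.** SAMPLE SIZE plans 15 infants per group. One infant reclassified changes that arm's BPD rate by 1/15 = 0.067, or 6.7 percentage points. With n infants assessed the step is 100/n points, so it is at least 6.7 when n is at most 15. This is the sensitivity of the rate to one misclassification from any cause. It does not estimate the bias or its probability.

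**The case against.** The strongest defence is that the sentence directly follows the commitment to blind outcome assessment, so the data it mentions may be outcome data only. The list under DATA COLLECTION AND STORAGE names no collector, and no section says in terms that the BPD tester abstracts delivery-room or 48-hour records. That uncertainty stands: the overlap of roles is the natural reading, not an explicit statement. The defence does not rescue the sentence, however, because the trial's own outcomes include the timing of VTV and PLV and the 48-hour ventilation measures. Only a reading limited to 36-week and later outcomes would preserve the blinding, and the plan does not state one.

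Four stronger conclusions that a reader might draw are not supported:

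- *That BPD assessment is unblinded.* The plan states that the tester is blinded. What is missing is a means of protecting that status.
- *That TV and PiP disclose the arm.* They only suggest it, for the reasons given with the table. Intervention infants switched to routine care after 60 seconds without measurable TV or VTV blur the pattern further.
- *That all longer-term outcomes lose their protection.* Discharge oxygen and long-term assessment do not depend on the combined role.
- *That BPD results will be biased.* This is a risk; the documents do not show that it occurs.

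It is also fair to say that the consequence here is small. The Phase II primary outcome is unaffected by who tests for BPD, no hypothesis tests are planned, and BPD is examined only for trends without power. Both arms receive routine VTV after 48 hours, so an infant's current support at 36 weeks need not give the arm away. The exposure comes through the records, which is why an access rule can address it.

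**Conclusion.** The concern holds in limited form. If the plan is followed as written, the masking of the 36-week physiologic BPD test cannot be relied on, because the same individual is assigned data collection, several required items identify or suggest the arm, and no access limit is set.

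This rests on two assumptions: that the data collected by that individual include the delivery-room and 48-hour items, and that no unwritten procedure already separates them from the tester. If either is wrong, a clarifying sentence is enough.

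The size of any bias cannot be derived from the documents. The improvement is desirable rather than essential for this pilot, and its main value lies in the planned reuse of the data.

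**What to change.** Make three changes:

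1. Assign collection of the delivery-room and 48-hour data to an investigator or the research coordinator who does not perform the BPD test.
2. Give the BPD tester no REDCap access to those forms or to allocation until testing is complete, and state this as an exception to the research team's full access.
3. Reword the BLINDING sentence so that blinding is claimed for the BPD test, the discharge-oxygen decision and the long-term assessment, and not for collection of ventilation data.

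The cost is REDCap permission settings and some scheduling. Treatment, sample size and endpoints do not change. No added assessor should be needed if the tasks can be divided among the roles the plan already names. That is an assumption: the coordinator is still to be appointed, and the documents do not show who is qualified to perform the test. The change masks the tester only; providers remain aware of the arm, as the plan already accepts.

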Secondary Hypothesis: We hypothesize that the TV generated via PLV in the immediate neonatal transition phase will be highly variable.

PHASE II:

Primary Hypothesis: We hypothesize that real time PiP adjustments are feasible when utilizing a T-Piece resuscitator to provide VTV for goal TV of 4-6ml/kg that can be seamlessly transitioned in the NICU.

Secondary Hypothesis:

- i. We hypothesize that infants receiving VTV will require lower PiP, will have lower oxygen needs with improved long term pulmonary morbidities
- ii. We hypothesize that VTV will have lower complication rates as compared to PLV.

SPECIFIC AIMS:

PHASE I:

Specific Aim #1: To assess feasibility of measuring TV in the DR for preterm infants <32 weeks with need for invasive positive pressure ventilation via endotracheal tube (ETT).

Objectives:

Date 10/15/2018
Protocol Version-I

- To assess the % infants with all equipment ready(including NM3 monitor and flow sensor) in DR to measure TV
- To assess the % infants where TV was measured within 60 seconds of ETT placement and positive pressure ventilation initiation.

Specific Aim #2: To assess variability in delivered TV in the DR with PLV for preterm infants <32 weeks with need for invasive positive pressure ventilation via ETT

Objectives:

- To assess the % infants with tidal within goal of 4-6ml/kg via routine PLV
- To assess the % infants with under or over ventilation using routine PLV
- To assess changes in TV with administration of surfactant with the same pressures

PHASE II:

Specific Aim #1: To assess feasibility of providing VTV, by quickly adjusting the peak inspiratory pressures (PiP) provided via the T-Piece resuscitator based on real time TV measurements.

Objectives:

- To assess the recruitment rates and successful enrollment into the study
- To assess the % of infants with measurable TV and successful adjustment of PiP to reach goal TV
- To assess the % of infants who fail VTV and need to be switched to conventional PLV

Specific Aims #2: To compare the pulmonary mechanics and physiology during VTV, respiratory support requirements

Objectives:

- To compare TV delivered during PLV versus VTV.
- To compare FiO2 requirement during PLV versus VTV
- Evaluate PiP, mean airway pressures (Paw), peak end expiratory pressures (PEEP) and oxygen requirement during the first 48 hours between the two study arms.
- Evaluate differences in blood gas results (pH, PCO2 levels).

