PHASE I: No specific withdrawal/termination criteria will be required as this is an observational study to assess feasibility of measuring tidal volume in the DR. Infant will continue to receive routine care as recommended by NRP, even if TV measurements are unsuccessful.

PHASE II: Control Arm: No specific withdrawal/termination criteria will be required, as these infant will continue to receive routine care per NRP recommendations without any study related intervention.

Intervention Arm: If TV cannot be measured or VTV cannot be provided within 60 seconds of initiating PPV via the ETT, the infant will be automatically switched to receiving routine care as recommended by the NRP.

INFORMED CONSENT PROCESS AND TIMING

Who: Parent.

When: "Deferred consent" is being requested after the birth of the child. The study process starts as soon as the baby is born and requires intubation as determined by the clinical team providing resuscitation. We will obtain a deferred consent from the parents only if the baby requires intubation in the delivery room and the TV measurements were obtained. We will approach the parents to use the data that was collected in the delivery room.

Rationale for deferred consent: *In an ideal situation, the consent should be obtained prior to study intervention. However, since the study intervention starts within few seconds to minutes of the baby's birth and it is not*

possible to determine which baby will need intubation in the delivery room, it would be unrealistic to have the opportunity to obtain informed consent we will aim for "deferred consent" process. As this study only present minimal risk to the infants and the device being used is an FDA approved device for use in neonates, a deferred consent is being requested for from the IRB.

How much time to decide: Since study related interventions has already occurred and we are asking parents to give consent for using this information as well as review of electronic medical records parents will have adequate time to make this decision free of any coercion to participate in the study.

Person authorized to obtaining consent: All investigators, program coordinator associated with the study.

SUBJECT FEES: None

REIMBURSEMENT/RENUMERATION FOR PARTICIPTION: None

RISK BENEFIT ASSESSMENT

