- The DR staff including the attending neonatologists, advanced practitioners and respiratory therapists will be trained and will have ample time to feel comfortable about the flow sensor and the Respirationics device prior to starting the study. Our staff currently uses a similar flow sensor device in the NICU and thus we do not anticipate any significant issues pertaining to training.

Subject stopping rules:

- Development of pneumothorax, pneumomediastinum
- PiP requirement >30 cm H₂O pressure for more than 60s
- Persistent low saturation or bradycardia with 60 seconds of optimum VTV

Individual responsible for stopping/modifying the protocol: **[name], MD**, Interim Division Chief along with the IRB will serve as the Safety Monitor for the study. Any SAEs will be reported to the IRB within 48 hours of occurrence.

POTENTIAL PITFALLS AND ALTERNATIVES

Inability to measure small tidal volume: As the *Respironics NM3 monitor* has never been tested to measure TVs in the range of 2-3ml/breath, we potentially run the risk of inability to measure the TV in this range in the extremely low birth weight infants (<500gm). We do plan to measure the TV in a standard test lung after acquisition of the device to ensure accuracy. Alternatively, we may have use the *Dräger Babylog VN500 ventilator* with a flow sensor device to measure TV in the DR. This will be more challenging as having a ventilator in the DR, but is possible to have one stand by, only to measure the TV from its circuit.

Leak from the ETT: Presence of a large leak may pose a significant problem in clinical situations as it makes accurate estimation of TV difficult. We will strictly adhere to the NRP guidelines for endotracheal tube sizes according the patients weight and gestational age and will evaluate both inspiratory and expiratory TV for the study. In situations with a large leak (>50%), we will use the expiratory TV as the marker for delivered TV.

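### The Phase II primary outcome, a loosely specified start time, does not measure the Phase II primary hypothesis, and infants switched at 60 seconds have no stated place in it

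*Combined protocol and SAP*

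**What the plan says.** All references are to the combined protocol and SAP.

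- **Primary Outcome Variable:** "Phase II: Timing of initiation of VTV will be similar to PLV". Nothing further is said about this variable. The Phase I outcome beside it does have an event and a 60-second window, and Data Analysis adds an 80% criterion for Phase I only.
- **Hypothesis, Phase II primary:** real-time PiP adjustment with a T-piece is feasible "to provide VTV for goal TV of 4-6ml/kg that can be seamlessly transitioned in the NICU".
- **Specific Aims, Phase II Aim 1 objectives:** "To assess the % of infants with measurable TV and successful adjustment of PiP to reach goal TV" and "To assess the % of infants who fail VTV and need to be switched to conventional PLV".
- **Withdrawal/Termination Criteria, intervention arm:** the switch to routine care applies "If TV cannot be measured or VTV cannot be provided within 60 seconds of initiating PPV via the ETT".
- **Data and Safety Monitoring:** where tidal volume is not measured within 60 s, "the patients will continue to receive conventional PLV during the time". The subject stopping rules there add later exits, for example "Persistent low saturation or bradycardia with 60 seconds of optimum VTV".
- **Study Endpoints:** "The study patient will continue in the randomized arm for the first 48 hours of life with ongoing data collection".
- **Data Analysis:** no formal hypothesis tests. Phase II is limited to point estimates such as means and proportions, with variability, and to recruitment and attrition rates. No timing analysis is named.

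**The concern.** Phase II is meant to show that VTV is feasible and so to justify a larger trial. The outcome labelled primary asks when VTV starts. The hypothesis asks whether the goal volume is reached by adjusting pressure, and whether that survives the move to the NICU. An arm could start VTV promptly, seldom reach 4-6 mL/kg, and still satisfy the primary outcome sentence.

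The outcome is also open where failures occur. An infant switched at 60 s may have no VTV start time, and nothing says whether that infant is dropped, given a limiting value or counted as a failure. An infant who starts on time and is later taken off VTV under a stopping rule has a good start time. Depending on choices made after the data are seen, failures could therefore be invisible in the result that carries the feasibility conclusion.

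**Working it through.** **1. The plan's own figure.** Sample Size (Phase II) says that with 30 patients the 95% interval is about 55% as wide as the standard deviation. This reproduces as the interval for a standard deviation s with 29 degrees of freedom: lower = s × √(29/45.72) = 0.796s, upper = s × √(29/16.05) = 1.344s, width = 0.548s. The figure is sound, but it describes how well a standard deviation is estimated. It does not bear on similar timing or on a success proportion.

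**2. Outcome against hypothesis.** The hypothesis needs three things: volume measured, goal reached under PiP control, and VTV carried into the NICU. The Aim 1 proportion covers the first two. A start time covers neither goal attainment nor transfer, unless initiation is defined as the first breath at goal.

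**3. Clock = first positive-pressure breath via the tube.** This is the clock of the switch rule, the only one attached to VTV in Phase II. On it PLV starts at about 0 s by construction. Suppose s of the 15 VTV infants are switched and the rule is applied as written.

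- *Switched infants left out:* each of the remaining 15 − s infants has a start time of at most about 60 s. The VTV minus PLV difference therefore lies between 0 and about 60 s for every s from 0 to 14.
- *Switched infants kept as >60 s:* the median is the 8th of 15 ordered values. It is at most 60 s when 15 − s ≥ 8, that is s ≤ 7, and becomes >60 s from s = 8.

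No distribution of start times is assumed. The handling of switched infants alone decides whether the summary can register failure.

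**4. Clock = intubation.** PLV start is then no longer 0 s by definition, and the outcome becomes a coherent question: does VTV delay the assigned ventilation? A prompt start still does not show that 4-6 mL/kg was reached.

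**5. Initiation = first breath at goal, switched infants kept as >60 s.** On the switch-rule clock, the timing data then yield the proportion at goal by 60 s. This reading comes close to the hypothesis, but the documents do not state it.

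**6. Precision of the matching proportion.** Exact (Clopper-Pearson) 95% limits for x of n = 15 are the 0.025 quantile of Beta(x, n − x + 1) and the 0.975 quantile of Beta(x + 1, n − x). The upper limit is 1 when x = n.

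| Successes | Proportion | Exact 95% CI | Width |
|---|---|---|---|
| 15/15 | 100% | 78-100% | 22 points |
| 12/15 | 80% | 52-96% | 44 points |
| 9/15 | 60% | 32-84% | 51 points |

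**The case against.** The strongest reply is that this is a pilot without formal tests, that both matching proportions are already Aim 1 objectives, and that Data Analysis plans to describe feasibility with proportions. They would be reported whichever measure is called primary. That stands, and it lowers the severity. It does not settle which result carries the feasibility conclusion, or what counts as reaching goal.

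Four stronger readings are tempting, and the documents do not support them.

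- *The outcome cannot be computed at all.* It is under-specified in these documents. VTV follows a predefined adjustment protocol (Intervention) that is not included here and may define initiation or goal attainment. The data list also has a general item for resuscitation details, which may hold the times.
- *VTV must always start later than PLV.* The Data and Safety Monitoring sentence is conditional on volume not being measured within 60 s. It does not say that every VTV infant begins on PLV. With breath-to-breath measurement, a VTV start near zero is not excluded.
- *Switched infants are ignored.* Their care is stated and Aim 1 counts them. Only their value in the timing outcome is missing. Study Endpoints suggests comparison by assigned arm, without saying that switched infants stay in the VTV arm for analysis.
- *An error rate is inflated.* No test is planned, so there is none to inflate.

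The consent text is a separate matter. Informed Consent Process and Timing seeks deferred consent only where volume was obtained. Vulnerable Population requires prior written consent in Phase II. Loss of measurement failures from the data would follow only under the former, so it is not evidence of the size of the present problem.

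**Conclusion.** The point holds as a mismatch and an incomplete definition; severity is should-fix. The named Phase II primary outcome does not measure the primary hypothesis. Event, time origin and the meaning of similar are not given in these documents, and switched infants have no stated timing value. The 0 to about 60 s bound, and the change in the median between 7 and 8 switched infants, rest on two assumptions: a clock starting at positive-pressure ventilation through the tube, and a switch rule applied as written. On an intubation clock these figures do not apply, but the mismatch remains unless initiation means the first breath at goal and switched infants are kept. What is at risk is the feasibility conclusion that is meant to justify the larger trial.

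**What to change.** - **Primary outcome:** among all infants randomised to VTV, the proportion with tidal volume measured and goal volume reached under real-time PiP control. Count unmeasured infants, and infants switched before reaching goal, as failures. Give an exact 95% CI.
- **Definitions in advance:** what counts as reached, whether an infant in range without any PiP adjustment counts, and the time window. Aim 1 has no time limit. The 60 s in the switch rule applies to measuring volume or providing VTV, so a 60 s limit for goal volume would be a new, stricter endpoint and should be labelled so.
- **Descriptive companions:** the proportion switched at 60 s or taken off VTV later, including those who had already reached goal, and maintenance of VTV through NICU transfer.
- **Timing:** keep as a secondary descriptive outcome, with initiation defined, one clock in both arms and switched infants kept as >60 s.
- **Comparison:** state that arms are compared as assigned, switched infants included. No non-inferiority margin is needed.
- **Separately:** reconcile the two consent sections with the IRB so that measurement failures are not lost from the denominator.

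None of this takes a position on the 60-second switch rule or the stopping rules. The cost is protocol wording, a few time stamps in both arms (tube placement, first positive-pressure breath, first goal volume), a possibly lower reported success figure, and an openly wide interval with 15 infants.
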